### 1.2 Secondary Objectives

1. To estimate the prostate specific antigen doubling time (PSADT) of the two treatment groups
2. To estimate the fraction of patients with a decrease in PSA of  $\geq 50\%$  from the start of treatment (PSA objective response rate) at 24 and 48 weeks.
3. To estimate the time to disease progression for both treatment groups by PSA progression as well as by radiologic disease progression (i.e. development of metastatic disease)

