### **5.4 Definition of Treatment Response and Disease Progression**

**Objective Response (OR):** Defined as a decrease of 50% or more in the PSA compared with the baseline level, confirmed by a second PSA at least 3-4 weeks later.

**Progressive Disease (PD):** Defined as:

- Radiographic Progression  
Radiographic progression for soft tissue lesions will be determined using RECIST 1.1. Radiographic progression for bone lesions will be determined by radionuclide bone scan using the consensus guidelines of the PCWG2 criteria, Or
- Unequivocal clinical progression: physical symptoms felt to be cancer related (in the opinion of the investigator), Or
- PSA Progression: Clinically significant increase in PSA as defined below.
  - *For subjects whose PSA declined from baseline (week 1 day 0):* record time from start of therapy to first PSA increase that is  $\geq 50\%$  and  $\geq 5$  ng/mL above the nadir, and which is confirmed by a second value  $\geq 3$  weeks later.
  - *For subjects whose PSA has not declined from baseline:* PSA progression has occurred if both:  
There has been a  $> 50\%$  increase over baseline (week 1 day 0), AND  
The value of PSA is  $> 5$  ng/mL above the baseline (week 1 day 0) value after 12 weeks

If subject's PSA progresses  $\geq 50\%$  and  $\geq 5$  ng/mL above the baseline (week 1 day 0) on Week 12, repeat the PSA at Week 14-16 to confirm rise. Subjects should continue taking study drug during this period, until the rise is confirmed. Once confirmed, subjects should either schedule Discontinuation Visit or start Open Label Extension treatment.

**Stable Disease (SD):** Disease Assessment that does not qualify as either objective response or progressive disease.

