### 11.1 Analysis Plans for Primary Objective

**PSA Slope:** Eligible patients must have a rising PSA with a minimum of 3 time points but up to 17 time points (2 rises at least 21 days apart) within the 12 months prior to study initiation (this could include the PSA measurement taken at the screening visit, but not at the baseline day 0 study visit). The pre-treatment slopes will be calculated based on these data prior to baseline (day 0). A minimum of three time points but up to five time points will be used for calculating on-study slopes: baseline, 12, 24, 36, and 48 week assessments. All data points will be used unless an assessment is unavailable, in which case the remaining time points will be used. There must be a minimum of three data points, and there will be no imputation of missing PSA values.

The primary objective will be based on the intent-to-treat (ITT) population and assessed with an ANCOVA model, with post-treatment PSA slope as the independent variable and study arm and baseline PSA slope as covariates. A two-sided t test at the 0.05 significance level will be used to determine if, adjusting for baseline, the post-treatment PSA slope has been reduced with MPX supplementation (Arm A). Scatterplots of post treatment PSA slope by baseline slope will be used to visualize the fitted ANCOVA model. Boxplots of the observed changes will also be used to visualize the results.

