## **11.2 Secondary Efficacy Assessment**

**PSA Doubling Time (PSADT):** The PSADT will be calculated as  $\ln(2)$  ( $=0.693$ ) /  $\beta$  ( $=$ slope of the linear regression fit to  $\ln$  PSA vs. time in months). If the patient's slope is less than or equal to zero, we will assign them a PSADT of 100 months, which is consistent with the literature.

A secondary statistical test of the difference between the two groups will be assessed by a nonparametric Wilcoxon Rank Sum test of the percentage change in PSADT (logarithm of the ratio of PSADT on-study divided by the pre-treatment PSADT). We will also analyze the log of the PSADT ratio by the analysis of variance (ANOVA) adjusted for the stratification factors. Confidence intervals (95%) for the change from baseline in PSADT will also be computed for the two dose groups. The paired t-test (or Wilcoxon signed-rank test) will be used to assess the within treatment group differences of PSADT on study compared to the baseline. Patients with negative slopes will be assigned PSADT of 100 months.

**PSA Reduction of  $\geq 50\%$  / Objective Response:** An objective response (OR) is defined as a decrease in PSA by 50% or more after the start of treatment. The objective response rate (ORR) is estimated as the fraction of men for whom an objective response is observed. The time to objective response, defined as the time from start of treatment to an observed objective response, as well as the average duration of response, defined as the time from objective response to disease progression, will also be summarized and compared between groups. To further summarize PSA responses, the percentage change in PSA from baseline at 24 and 48 weeks will be presented in the form of waterfall plots.

**PSA Progression:** The distribution of time to PSA progression will be estimated using Kaplan-Meier method for both treatment groups combined and separately. The stratified logrank test will be used to test the hypothesis that the time to PSA progression distributions for the 2 treatment groups are the same. The same stratification factors used for the randomization will be used to stratify the logrank test.

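### Objective response is defined three ways (confirmed in Section 5.4, unconfirmed in Section 11.2, at fixed weeks in Section 1.2), and its duration is compared between arms although only responders have one

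*Combined protocol and SAP*

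**What the plan says.** Three places in the protocol describe the PSA response endpoint.

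- **Section 1.2 (secondary objective 2)** asks for the fraction of men with a fall of at least 50% "from the start of treatment (PSA objective response rate) at 24 and 48 weeks".
- **Section 5.4 (definitions)** requires a fall of at least 50% from the baseline level, "confirmed by a second PSA at least 3-4 weeks later".
- **Section 11.2 (analysis)** states: "An objective response (OR) is defined as a decrease in PSA by 50% or more after the start of treatment". The estimator follows: "The objective response rate (ORR) is estimated as the fraction of men for whom an objective response is observed". There is no confirmation and no pointer to Section 5.4. Weeks 24 and 48 appear only for the waterfall plots, and the denominator population is not named.

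Section 11.2 then adds two timing summaries. Time to response is "defined as the time from start of treatment to an observed objective response". The second is duration: "the average duration of response, defined as the time from objective response to disease progression, will also be summarized and compared between groups". Neither has a stated method or censoring rule, although the same section specifies Kaplan-Meier estimates and stratified logrank tests for PSA progression and disease progression.

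**The concern.** An analyst following Section 5.4 would drop a man with a single low value. One following Section 11.2 would count him. One following Section 1.2 might count him only if the fall is present at week 24 or week 48. These can be three different rates for one stated secondary objective, and the choice could be made after the data are seen.

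Confirmation is more than a formality here. Section 3.1 admits men after surgery with a PSA just above 0.2 ng/mL, where a 50% fall is a change of about 0.1 ng/mL. One low reading can then make a responder.

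Duration raises a separate problem. The clock starts at response, so men who never respond have no value. If MPX changes who responds, the responders in the two arms are different kinds of men, and a difference in mean duration cannot be read as a treatment effect. A simple average also has no defined value for a responder who has not progressed.

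**Working it through.** The plan gives no expected response rate or power for this endpoint, so there is no stated figure to reproduce. The check compares the texts and then sizes the consequence.

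**1. The three wordings side by side**

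| Element | Section 1.2 | Section 5.4 | Section 11.2 |
|---|---|---|---|
| Fall of at least 50% | yes | yes | yes |
| Second PSA required | not mentioned | yes | no |
| Timing | weeks 24 and 48 | not fixed | any time after start |
| Denominator | patients | none given | men |

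**2. Weight of one man.** Section 5 plans 40 per arm, so one man is 1/40 = 2.5 points. (With the 39 per arm of the power calculation it is 1/39 = 2.6.) One responder is 2.5% (exact 95% interval 0.1 to 13.2%); two are 5.0% (0.6 to 16.9%).

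**3. How many responders to expect.** Section 2.2.3 reports one fall of at least 50% in the phase II 4,000 mg group. The size of that group is not stated there; 112 men allocated 1:2:2 gives 112 × 2/5 = 44.8, taken as 45. The assumed rate is 1/45 = 2.2%.

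- Expected per arm: 40/45 = 0.89.
- No responder in an arm: (44/45)^40 = 0.407.
- At least one responder in both arms, same rate in each: (1 − 0.407)² = 0.35.

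That phase II group was not selected for the AA genotype, so a wider range is shown, again with the same rate in both arms:

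| True rate | Expected per arm | At least two responders in both arms |
|---|---|---|
| 2.2% | 0.9 | 5% |
| 5% | 2 | 36% |
| 10% | 4 | 85% |
| 20% | 8 | 99.7% |

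**4. Effect of confirmation on the rate.** The share of single falls that would be confirmed is not in the documents. If it is 50 to 90% (assumed), an unconfirmed 10% becomes 0.10 × 0.5 = 5% to 0.10 × 0.9 = 9%.

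**5. Can the schedule confirm a response?** On-study PSA is taken at "baseline, 12, 24, 36, and 48 week assessments". With windows of ±7 days, consecutive visits are at least 84 − 14 = 70 days apart, well beyond the interval in Section 5.4. A fall at week 12, 24 or 36 can be confirmed at the next visit. For a fall first seen at week 48 no further PSA is scheduled on blinded treatment. The Study Calendar's 28-day visit follows the last dose, so it is off drug for men who stop, and comes only after open-label MPX for men who enter the extension.

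**6. Will durations be complete?** As an illustration, let a man's PSA fall exactly 50% from baseline B by week 12 and then regrow at the 6- or 15-month doubling times of Section 11. Week 48 is 36 weeks, or 8.3 months, later. The growth factor is 2^(8.3/6) ≈ 2.6 or 2^(8.3/15) ≈ 1.47. Section 5.4 requires a rise above nadir of at least 50% and at least 5 ng/mL. At 15 months the 50% condition is not met. At 6 months the rise is 1.6 × B/2 = 0.8B, so B must exceed about 6.2 ng/mL. Unless radiographic or clinical progression comes first, many responders would still be progression-free at week 48.

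**The case against.** Section 5.4 is the protocol's definitions section, and Section 11.2 relies on it elsewhere: it uses PSA progression without restating the criteria. So Section 11.2 may be shorthand for the confirmed response. That is possible, but Section 11.2 offers its own definition instead of citing one, and its estimator speaks of a response being observed. The text therefore permits the unconfirmed reading, and a cross-reference is needed.

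Several stronger readings are tempting, and the documents do not support them.

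- *Section 11.2 has no reference value.* It measures the fall after the start of treatment, its waterfall plots use change from baseline, and the Study Calendar notes require a day 0 PSA for on-study calculations. Day 0 is the evident reference.
- *Time to response is also a responder-only comparison.* Its clock starts with treatment, so every randomised man can contribute, censored if he does not respond. What is missing is the method.
- *The phase II response was an unconfirmed value, or one or two such values would make up the whole difference between arms.* Section 2.2.3 does not say whether that response was confirmed, and no difference can be known in advance.
- *Durations are cut off at week 48.* PSA continues every 12 weeks in the open-label extension, and whether those values count is simply not stated.

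It also stands that the response rate is only to be estimated, that no between-arm test of it is specified, and that Section 11.4 places everything but the primary outcome outside the confirmatory claim.

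**Conclusion.** The inconsistency is real and lies in operative text: Sections 1.2, 5.4 and 11.2 do not define the same endpoint. Each man affected by confirmation is worth 2.5 points in an arm of 40. If the phase II rate carries over, fewer than one responder per arm is expected, so the definition could decide whether an arm shows any response at all. That expectation rests on a derived denominator of 45 and on men not selected by genotype. At 10 to 20% the issue shrinks but remains.

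The between-arm comparison of average duration is not protected by randomisation, has no rule for responders without progression, and at the phase II rate would have responders in both arms only about 35% of the time. Its end point also needs settling: Section 5.4 counts PSA, radiographic and clinical progression, while Section 11.2 labels disease progression as metastatic disease.

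The change is worth making, but the stakes are modest. These are unadjusted secondary analyses, and the primary slope ANCOVA does not depend on them.

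**What to change.** - **One definition in Sections 1.2, 5.4 and 11.2.** Use the confirmed response of Section 5.4, relative to the day 0 PSA, with all randomised men as denominator. State whether weeks 24 and 48 mean response by that week or at that week, and whether a response is dated at its first or its confirming PSA.
- **Confirmation rule.** A fall at week 12, 24 or 36 is confirmed by the next scheduled blinded PSA. A fall first seen at week 48 is counted as unconfirmed and reported separately. Single-value falls are shown in the waterfall plots.
- **Duration of response.** Describe it by arm without a between-arm test. Name the progression events that end it, and state the censoring rule for men who have not progressed, including whether extension data count.
- **Time to response.** If the arms are compared, include all randomised men from the start of treatment, with non-responders censored.

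The cost is wording in the protocol and analysis plan; no extra PSA draw is needed. The reported response rate may be slightly lower, because some single falls, including all those first seen at week 48, will not count.

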## **11.3 Correlative Studies**

Correlative studies seek to improve understanding patient response to MPX, as well as the biological mechanism or mechanisms of action. Correlative studies include: (1) correlating PSA

response with antioxidant levels and (2) correlating PSA response with markers of oxidative stress.

We will look at baseline (prior to drug administration on Week 1 Day 0), week 12, week 24, week 36, week 48 and progression levels of selenium, lycopene, and  $\alpha$ -tocopherol. Three measures of oxidative stress (F2-Isoprostanes, 8-OHdG, and Malondialdehyde) taken at all three time points (baseline, week 12, week 24, week 36, week 48 and progression) will be compared by study arm for changes following treatment. Comparisons will be visualized using boxplots of the raw data on a logarithmic scale. Analytic comparisons will be made with multivariable regression analysis using generalized estimating equations (GEE) to assess oxidative stress outcomes as a function of MPX treatment, time, and other factors such as Gleason score, baseline PSA, and age. A compound symmetric covariance structure will be assumed for these regression models. With sample sizes of 40 per group, a standardized effect size of 40% would be detectable with 85%-96% power assuming within-subject correlations of 0.10-0.30 and a two-sided alpha of 0.10. Although multiple generalized estimating equation models will be explored, one for each measure of oxidative stress, we will not adjust for multiple comparisons.

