### **5.2 Blinding**

The double-blind portion of the study will end when every subject has either completed the study, been treated for 48 weeks, or discontinued the study. A subject is considered to have completed the study if he experiences PSA progression as defined in section 5.4. A subject will also be considered to have completed the study if they have not experienced PSA progression but remain on-study at the time the study ends at 48 weeks. Patients will not be informed if they are on the MPX or placebo arm. At protocol defined progression or completion of 48 weeks of treatment, patients will be offered an additional four 12-week cycles of MPX treatment, and will come for a visit every 12 weeks, without correlates but with PSA drawn every 12 weeks. Patients who come off study for any other reason will not be offered open label, extension MPX. Subjects will have an end of study visit and are required to have CT and bone scans prior to beginning the open label extension, and at discharge.

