### 9.2 Serum

Blood for measuring serum levels of antioxidants (selenium, lycopene, alpha-tocopheral) and oxidation marker MDA will be collected from the 80 randomized patients at Day 0 (prior to first dosing), 12-, 24-, 36-, 48-Week, and Primary Discontinuation (progression) Visits, see Study Calendar. Baseline sample on Day 0 Visit should be collected before patient receiving study drug. All other visits, blood samples should be drawn at least one hour post dose in the morning (preferably before noon).

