## 10. STUDY CALENDAR^18

Treatment Period	Pre-Screen for AA	Screen for Elig. 	On Study Visits -Blinded					Open Label Extension 		28-Day Follow Up 
			Weeks	Day -28 to day -1	W 1 day 0	12 W $\pm$ 7 days	24 W $\pm$ 7 days	36 W $\pm$ 7 days	48 W or Primary DC  $\pm$ 7 days	
Informed Consent	√									
Inclusion/Exclusion Criteria 		√								
Medical History 		√								
Pathology Review		√								
Complete physical examination		√					√		√	
Interval History and Brief physical examination 		√		√	√	√		√		√
Vital Signs (temperature, BP, heart rate)		√	√	√	√	√	√	√	√	√
Weight		√	√	√	√	√	√	√	√	√
Height		√								
ECOG Performance status		√	√	√	√	√	√	√	√	√
CMP 		√		√	√	√	√	√	√	√
CBC w/diff.		√		√	√	√	√	√	√	√
Urine Creatinine 			√ 	√	√	√	√			
PSA		√ 	√ 	√	√	√	√	√	√	√
CT/Bone Scan 		√					√		√ 	
Testosterone		√								
Blood for MnSOD genotyping 	√									
Serum Collection for Correlative Studies 			√ 	√	√ 	√	√			
Rectal Swab for Correlative Studies			√ 	√	√	√	√			
Urine Collection for Correlative Studies			√ 	√	√ 	√	√			
Adverse Event Assessment			√	√	√	√	√	√	√	√

Concomitant Medication		√	√	√	√	√	√	√	√	√
Dispense Study Drug and Pill Diary			√	√	√	√		√ 		
Collect Returned Study Product and Pill Diary 				√	√	√	√	√	√	
Food Frequency Questionnaire and Dietary Supplement List 			√	√	√	√	√			

 **Screening window:** Baseline evaluations are to be conducted within 4 weeks prior to start of protocol therapy. Scans are allowed within 90 days. CT of chest, abdomen and pelvis. With contrast preferred; but without contrast allowed.

 **Open label extension:** Patients on study drug who complete protocol requirements may choose to start MPX after completing 48 weeks on the blinded portion of the study or after discharge with documentation of protocol defined progression (per Section 5.4). In order to remain a double-blinded trial, patients and investigators will not know to which arm they were assigned and thus it is patient and investigator judgement if they want to try unblinded MPX for up to an additional 48 weeks.

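### The 85%-96% power for the oxidative-stress markers fits five measurements that all carry the treatment effect; the schedule gives at most four, and the contrast and role of baseline are not stated

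*Combined protocol and SAP*

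**What the plan says.** Section 11.3 plans a GEE regression for each of three oxidative-stress markers (F2-isoprostanes, 8-OHdG, malondialdehyde) under a compound symmetric covariance. The power statement is that "a standardized effect size of 40% would be detectable with 85%-96% power assuming within-subject correlations of 0.10-0.30 and a two-sided alpha of 0.10", preceded by "With sample sizes of 40 per group".

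The measurements are described as "taken at all three time points (baseline, week 12, week 24, week 36, week 48 and progression"), which announces three time points and lists six. The arms are to be compared on how the markers change after treatment. The outcomes are modelled "as a function of MPX treatment, time, and other factors such as Gleason score, baseline PSA, and age". No arm-by-time term is named. The text does not say whether the baseline marker level is an outcome, a covariate or a value to subtract.

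The sampling rules are elsewhere:

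- Section 9.2: "Baseline sample on Day 0 Visit should be collected before patient receiving study drug". Section 9.3 has the same rule for urine.
- Section 10 puts the last blinded visit in one calendar column, "48 W or Primary DC".
- Section 5.2: "A subject is considered to have completed the study if he experiences PSA progression as defined in section 5.4". The open-label extension takes no correlative samples.
- Section 5.4: once PSA progression is confirmed, a man goes to the discontinuation visit or into the extension.

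**The concern.** A power figure for repeated measures depends on how many measurements carry the effect and on which contrast is tested. Section 11.3 gives neither, and its own count of time points contradicts its list. The range printed there appears to need five measurements that all reflect treatment, whereas a man can give at most four after dosing.

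The model terms raise a second question. Baseline is listed among the time points, and only treatment and time are named besides the other factors. If Day 0 enters as an outcome and the treatment main effect is tested, that coefficient averages in a sample on which treatment cannot have acted. A reader then cannot tell what difference the marker analyses can detect. With three markers tested at two-sided 0.10 and no multiplicity adjustment, leaving the contrast open also allows it to be chosen after the data are seen.

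**Working it through.** **Inputs.** From Section 11.3: n = 40 per arm, effect 0.40, correlation rho from 0.10 to 0.30, two-sided alpha 0.10 (critical value 1.645), compound symmetry. I take 0.40 as SDs of one measurement and assume complete data.

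**Formula.** Power = Phi(d / sqrt(2v/n) − 1.645), where d is the arm difference and v is the per-man variance of the quantity compared, with a single measurement having variance 1.

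**Step 1: reproduce the stated range.** For the mean of K measurements that all carry the full effect, v = (1 + (K − 1)rho)/K.

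| K | rho 0.10 | rho 0.30 |
|---|---|---|
| 3 | 88.2% | 78.9% |
| 4 | 93.2% | 82.9% |
| 5 | 95.9% | 85.4% |
| 6 | 97.3% | 87.0% |

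For K = 5 and rho = 0.30: v = (1 + 1.2)/5 = 0.44, the standard error is sqrt(0.88/40) = 0.148, and 0.40/0.148 − 1.645 = 1.05, so power is 85.4%. Of these rows only K = 5 rounds to 96% and 85%. With 39 per arm, the number in the Section 11 sample-size paragraph, K = 5 gives 95.5% and 84.6%, so 39 or 40 makes no real difference.

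**Step 2: count the post-dose samples.** Weeks 12, 24 and 36 give three. The shared week-48-or-discontinuation visit gives a fourth. Confirmed progression ends blinded participation and the extension takes no correlates, so there is no fifth. The only other route to five counts Day 0, which is pre-dose.

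**Step 3: power under each reading of the plan.**

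| Reading | d | v | rho 0.10 | rho 0.30 |
|---|---|---|---|---|
| Stated | – | – | 96% | 85% |
| Mean of four post-dose values, baseline unused | 0.40 | (1 + 3rho)/4 | 93.2% | 82.9% |
| Baseline as fifth outcome, treatment main effect | 0.40 × 4/5 = 0.32 | (1 + 4rho)/5 | 85.5% | 69.6% |
| Four post-dose values, baseline as covariate | 0.40 | (1 + 3rho)/4 − rho² | 93.9% | 89.2% |
| Post-dose mean minus baseline, unadjusted | 0.40 | (1 + 3rho)/4 + 1 − 2rho | 51.7% | 60.5% |

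At rho = 0.30, baseline as an outcome gives 0.32/0.148 − 1.645 = 0.51, or 69.6%. Baseline as a covariate has v = 0.475 − 0.09 = 0.385, a standard error of 0.139 and 0.40/0.139 − 1.645 = 1.24, or 89.2%.

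If the 40% means SDs of change, change scores under compound symmetry correlate 0.5 whatever rho is. Then v = (1 + 3 × 0.5)/4 = 0.625 and power is 73.2%.

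**Step 4: simulation check.** With 20,000 simulated trials per correlation (rho 0.10 / 0.30): five full-effect measurements 95.7 / 85.4; four post-dose 93.2 / 83.2; baseline as outcome 85.5 / 69.7; baseline as covariate 93.6 / 88.8; unadjusted change 52.5 / 60.7.

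**Step 5: attrition, as assumptions.** With baseline as a covariate, losing 10% of men (36 per arm) gives 91.6% / 86.2%. Losing 20% (32 per arm) gives 88.6% / 82.5%.

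**The case against.** The strongest reply is that nothing is miscalculated. The printed range can be reproduced from its own inputs, and the five-measurement model is an inference. Going from five samples to four costs only 2 to 3 points, while the plan's own correlation range moves power by 11. The recommended analysis gives 89% to 94%, which lies inside the stated range. The larger losses need choices the plan does not make: the covariate list is open-ended, and comparing change by arm points away from a diluted main effect. Sections 9.2, 9.3 and 11.3 also list week 48 and progression separately, which could be read as five post-dose points. Finally, these are tertiary markers, and this figure does not set the sample size.

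Much of this stands. The five-to-four loss is small, the 70% and the 52% to 61% are conditional, and the consequence is confined to exploratory analyses. Two parts do not stand. The separate listing of week 48 and progression gives no individual man a fifth sample, because the calendar and the progression rules make them alternatives. And an open list of factors does not settle the role of baseline: the text puts the pre-dose sample among the time points, and a model with only the named treatment and time terms would dilute the effect.

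**Conclusion.** The concern holds. The stated 85% to 96% corresponds to five full-effect measurements, and the schedule supplies at most four. None of the four readings in the table, with the 40% in SDs of one measurement, rounds to the stated range at both ends. The shortfall is 2 to 3 points if only the four post-dose values are used, and about 15 points at a correlation of 0.30 if baseline is kept as an outcome under one treatment coefficient. The main defect is therefore the unstated contrast and role of baseline, more than the count of samples.

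This rests on 40 men per arm with complete data, compound symmetry, an equal effect at every post-dose visit, and 0.40 read as SDs of one measurement. The plan's own calculation is not shown, so its basis is inferred. The primary analysis is untouched.

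**What to change.** In Section 11.3:

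- Make weeks 12, 24, 36 and 48 (or discontinuation) the GEE outcomes, with the baseline level of the same marker as a covariate.
- Name the average post-dose difference between arms as the tested contrast.
- State that up to four post-dose measurements per man contribute, and which SD defines the 40% effect.
- Restate power as about 89% to 94% with 40 per arm before attrition, and add a figure for whatever loss the sponsor expects.
- Replace the reference to three time points with the scheduled list.

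This changes wording only. The baseline samples are already scheduled and no visit is added. The upper power figure falls from 96% to about 94%, and the lower rises from 85% to about 89%.
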